**PSIY-511-15: Adapting and Evaluating Dialectical Behaviour Group Therapy
for Adults with Dual Diagnosis (Intellectual Disabilities with Psychiatric
Disorder)**

NCT02919826

4 Dec 2017

Study Protocol & Statistical Analysis

Present study

The present study is a pilot community-based, double blind, randomized controlled trial of an adapted DBT skills group and program for individuals with Intellectual and Developmental Disabilities (IDD) and psychiatric illness. The purpose of this study was to clinically evaluate and empirically determine the feasibility and effectiveness of delivering an adapted DBT community-based skills group to adults with intellectual disability and transdiagnoses. Dykstra and Charlton's work, *Dialectical Behavior Therapy Skills Training: Adapted for Special Populations* (DBT-SP; written in 2004 and revised in 2008; Dykstra & Charlton, 2008, Charlton & Dykstra, 2011), was the basis from which the adapted DBT manual and program (i.e. aDBT-ID) was used in the present study. As part of a community based DBT program, in addition to the manualized skills group, other components included mental health treatment i.e. psychiatric medication and consultation, individual therapy, crisis services, caregiver coaching and team consultation for both the researchers and clinicians.

Methods

Participants

A community based sample of 19 adults with mild to moderate IDD and transdiagnoses i.e. co-morbid psychiatric disorders participated in the present study. Inclusion criteria were: age 18-65 years old, administratively confirmed diagnosis of mild to moderate IDD, co-morbid psychiatric diagnoses and history of emotional and behavioural concerns and lead agency commitment i.e. allocated caregiver to attend all sessions. Exclusion criteria included a diagnosis of autism spectrum disorder or acute psychosis interfering with daily functioning.

The group participants comprised of 9 males and 10 females; ages ranging from 22 to 34 with one 52 year old. All were referred with confirmed diagnoses of mild (16) to moderate (3) IDD established by their administrative eligibility for support services i.e. DSM-V criteria for IDD. All lived in either residential treatment homes (3), group homes (5), host family home (2) or independent living either alone (4) with a roommate (2), with their parents (2) or a spouse (1).

Co-morbid psychiatric diagnoses upon referral (not mutually exclusive) included Personality Disorders (BPD 10, Mixed PD 2), Mood Disorders (Depression 2, Anxiety 8, Bi-Polar 3, OCD 2), Psychotic Disorders (2), Childhood Disorders (ADHD/ADD 7), Trauma Disorders (PTSD 4), Substance Abuse Disorder (1), Sexually Problematic Behaviour/Pedophilia (2), Acquired Brain Injury (1), Seizure Disorder (2) and Speech and Language Disorder (1). All participants were identified as having significant problems with emotional dysregulation and chronic interpersonal difficulties with family, friends and caregivers. In addition, the majority

were experiencing behavioural difficulties with anger that impacted their daily functioning. All participants had a medication regime including a range of psychotropic medications for behavioural control and mental health stability (e.g. anti-psychotics, anti-depressants, anti-anxiety, mood stabilizers) and treatments for associated physical health conditions (anti-convulsants, diabetes medication).

Clinical services outside of the group included psychiatric medication oversight for all participants except four who had family physicians prescribing. All participants had regular therapy or treatment interventions with either assigned social workers, psychologists, behaviour therapists, nurse or addiction counsellors. Also, participants had a variety of tertiary care team involvement including specialization in either dual diagnosis, mental health crisis, assertive community treatment and 24 hour access to mental health crisis lines. Some participants had regular legal oversight from either court diversion workers or probation officers.

A total of 22 caregivers participated in the group trial, with n=14 completing assessments. Caregiver participants were comprised of both men and women from a range of developmental and mental health agencies. Majority were front line staff or direct support workers (14) apart from two behaviour therapists, two social workers and two family members. One participant had two workers attend due to his need for supervision. Most of the caregivers had known the clients for less than three years (15), with three knowing their clients between 3-10 years and one for over 10 years. The amount of client contact ranged from 1-3 days a week (8) to 3-7 days a week (7) to bi-weekly or monthly (4). The duration of each contact ranged from intermittent daily contact (9), to 2-3 hours contact (6) to one-to-one counselling (4). The latter proportions likely influenced by living situation (e.g. group homes, host family and independent living) and type of contact (e.g. direct support hours, consultation services or therapy sessions.)

Procedure

Following ethical approval, clients and caregivers were recruited through partnering developmental and mental health agencies that provide support services to persons with IDD, and through expression of previous interest by affiliated mental health professionals. Additionally, information letters were distributed to agencies who had expressed an interest in available treatment services. All referred respondents were then screened for eligibility based on inclusion and exclusion criteria using administrative data and informant interview. Once eligible participants were identified and consent obtained, they were asked to invite their preferred caregiver to attend the group with them. Subsequently, caregivers were either given or sent a letter of information and consent form for attendance. Written consent was confirmed at pre-assessment; with consent for participant involvement including the use of a multi-modality approach of both written text and verbal discourse.

Participants and caregivers were then de-identified and randomly assigned utilizing a relevant software (Randomizer.org; or “Research Randomizer”) with the researcher blind to group identities. Randomization occurred once a dozen participants were recruited and then again prior to the second group to accommodate rolling recruitment. Participants were initially allocated to either the treatment group or waitlist control group for one of the three sequential groups. All participants attended their assigned group except for one who requested an earlier group due to travel limitations and one replacement for the last group following client attrition.

Measures

Participation in the aDBT-ID trial was initiated by recruitment letters and by convenience sampling through partnering agencies. Referrals were initially screened for eligibility criteria e.g. level of ID and ASD, and availability of both client and caregiver for the trial and time commitment required for group randomization and attendance. Upon referral and consent by both client and caregiver, an interview was conducted by a research assistant (independent from the research team and blind to the group allocation) who confirmed eligibility and obtained written consent. The interview was completed prior to randomization to one of the three groups, and one month prior to group commencement. The interview included a demo-graphic questionnaire which included information on age, gender, locality, living arrangements, affiliated agency, caregiver role and experience, diagnoses, medications, and existing clinical services and supports.

After the questionnaire, a two part assessment involving an interview and psychometric measures was conducted. The interview conducted with clients to identify insight into their own emotional and behavioural difficulties, and their motivation to gain coping skills with these difficulties. Caregivers were also interviewed about their perspectives of the client’s overall profile and need for treatment. The second part included a battery of both psychometric and observational measures to gather baseline measures of client emotional regulation, anger control and psychopathology. Standardized measures included the Difficulties in Emotional Regulation Scale (Gratz & Roemner, 2004), Novaco Anger Scale: Provocation Inventory (Novaco, 2003), and Reiss Scale of Dual Diagnosis (Reiss, 1990), respectively. The caregiver interview aimed to identify what they perceived the presenting problems to be, the effect of the issue(s), how they addressed the issue with the participant, and coping strategies currently utilized. The matched caregiver pre-assessment measures included the Emotion Regulation Checklist (Cicchetti & Shields, 1997; adapted with written permission by Cicchetti, 2016), Novaco Anger Scale: Provocation Inventory (Novaco, 2003) and Reiss Scale of Dual Diagnosis (Reiss, 1990). Measures were completed in relation to caregiver perspectives of clients’ profiles of emotional regulation, anger control and mental health difficulties. The psychometric measures noted above all have robust validity indices as noted in their respective manuals.

Following group treatment, interviews and post assessments were conducted by independent research assistants, with both participants and caregivers, within approximately four weeks of group completion. In addition to re-administered assessments to measure potential change, the post-interview included an update and feedback questionnaire that focused on their qualitative experiences participating in the group, what they learned, whether they believed the skills presented would benefit their daily lives, coping strategies that they were currently utilizing, and feedback regarding suggested changes to the group. They were also asked about any significant changes in their circumstances since their group attendance (e.g. residential moves, hospitalizations, or legal charges) to illustrate possible contributory attrition factors if applicable. Also administered was an adapted multiple choice questionnaire, the Global Impression of Change: aDBT-ID. The measure was adapted from the Patients Global Impression of Change Scale (Hurst & Bolten, 2004) and then reviewed with the research team for face validity. The questionnaire identified the initial presenting problems and then measured both client and caregiver perspectives of overall change following the group, and for each respective module; with five responses ranging from no change to significant change. Accordingly, the interviews with the caregivers matched the clients' post assessment with the psychometric measures, feedback interview and GIC questionnaire.

Statistical Analysis

Outcomes for the group were evaluated using both quantitative and qualitative measures in order to identify any group treatment changes; but also to assess the experiences by both clients and caregivers in the treatment process and their views on participation in community-based research. Given the small sample group and attempts at research rigour, quantitative measures were analysed utilizing an 'intent to treat' paradigm such that all participants who started the group were included in analysis. Using a mixed method ANOVA within SPSS v24, group differences, within and between, were assessed using non-parametric analysis due to group composition i.e. Wilcoxon signed-rank and Man-Whitney U tests, respectively.

Qualitative measures were evaluated using thematic analysis (Braun & Clarke, 2006) for both client and caregiver interviews to identify and illustrate thematic patterns through an iterative process of data immersion, category generation and theme identification followed by inter-rater verification.

Post-assessment data was unable to be obtained for one participant and one caregiver, and as such both qualitative and quantitate components were conducted with a sample size of N=18.

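### The trial is labelled double blind, but the clients and attending caregivers know whether and when treatment was received, and they supply every named quantitative outcome

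*Combined protocol and SAP*

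**What the plan says.** The opening section, Present study, calls the trial a "double blind, randomized controlled trial of an adapted DBT skills group" without saying which parties are blinded. It also gives effectiveness, alongside feasibility, as a purpose.

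On what clients and caregivers experience:
- Procedure says clients were first allocated to "either the treatment group or waitlist control group" across three sequential groups. No sham or attention control is described.
- Participants makes it an inclusion criterion that the lead agency commit an "allocated caregiver to attend all sessions".

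On blinding:
- Procedure says random assignment was done "with the researcher blind to group identities".
- Measures describes the research assistant at the pre-treatment interview as "independent from the research team and blind to the group allocation". It then adds: "The interview was completed prior to randomization to one of the three groups".
- Measures describes the research assistants at post-assessment as independent. It does not say they were blind.

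On who supplies the outcomes, Measures lists three scales for clients and three matched scales for caregivers. Of the caregiver set it says "Measures were completed in relation to caregiver perspectives of" the clients' profiles. The Global Impression of Change is obtained from both after the group.

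**The concern.** In ordinary use, double blind tells a reader that neither the people treated nor those who assess them knew the allocation. A reader who accepts the label will treat differences on the emotion regulation, anger and psychopathology scales as protected from rater expectation.

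Here the raters are the people who sat through the sessions or were still waiting for them. A client who has completed a skills group, or a caregiver who has given time to every session, may rate more favourably for reasons unrelated to any real change. Nothing in the documents guards against this, and both the within-group and the between-group tests would pick it up as an effect.

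**Working it through.** The documents give no figure to reproduce on this point. The main check sets the statements side by side. A simulation then gives a sense of scale.

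**Who could be blind, and when**

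| Party | What the document says | Blind when post-treatment ratings are given? |
|---|---|---|
| Client | Attends the group or waits (Procedure) | No. One participant asked for an earlier group, so timing was known |
| Caregiver | Must attend every session (Participants) | No |
| Researcher | Blind at random assignment (Procedure) | Not stated; not described as a rater |
| Pre-treatment interviewer | Blind to allocation (Measures) | Not applicable: the interview preceded randomization, so there was no allocation to know |
| Post-assessment staff | Independent (Measures) | Not stated. Their interview asks about experience of the group, which would reveal attendance |

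**Who supplies each named quantitative measure**

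| Instrument | Client | Caregiver |
|---|---|---|
| Difficulties in Emotional Regulation Scale | yes | – |
| Emotion Regulation Checklist | – | yes |
| Novaco Anger Scale: Provocation Inventory | yes | yes |
| Reiss Scale | yes | yes |
| Global Impression of Change | yes | yes |

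So 5 of 5 named instruments come from the client, the caregiver or both. That is 3 + 3 = 6 scale sets plus the change questionnaire. None is assigned to a blinded independent rater. Caregiver rating is explicit; client self-rating is inferred from the contrast with the matched caregiver set. Baseline ratings precede randomization, so the exposure is in post-treatment ratings and anything computed from them.

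**Illustration of scale**

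Assumptions, none of them in the documents: normal data with SD 1 at each time; no true effect; a bias *b* of 0.2 or 0.4 SD added to one arm's post score; pre-post correlation *r* of 0.6 or 0.7; two-sided 5% level; arm sizes as shown. The test is the exact Mann-Whitney, with 200,000 simulated trials per cell.

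The SD of a change score is √(2(1 − r)):
- r = 0.6: √0.8 = 0.894
- r = 0.7: √0.6 = 0.775

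The standardized shift is *b* divided by that SD:
- *b* = 0.2: 0.2/0.894 = 0.22 and 0.2/0.775 = 0.26
- *b* = 0.4: 0.4/0.894 = 0.45 and 0.4/0.775 = 0.52

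Proportion of trials significant:

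| Arms | No bias | b = 0.2, change scores (r = 0.6; 0.7) | b = 0.4, change scores (r = 0.6; 0.7) | Post scores only (b = 0.2; 0.4) |
|---|---|---|---|---|
| 9 vs 9 | 0.040 | 0.059; 0.065 | 0.119; 0.147 | 0.055; 0.103 |
| 12 vs 6 | – | 0.058; 0.065 | 0.112; 0.136 | – |
| 7 vs 7 | 0.038 | 0.052; 0.056 | 0.094; 0.113 | 0.049; 0.083 |

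The first two rows split the analysed N = 18 in Statistical Analysis. The 7 vs 7 row splits the caregivers, reported in Participants "with n=14 completing assessments". That count is not reconciled with Statistical Analysis, which reports post-assessment data missing for one participant and one caregiver and gives N = 18.

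**The case against.** The strongest reply is that the label was never defined and may refer to the two parties Procedure and Measures do call blind: the researcher and the pre-treatment research assistant. On that reading the fault is an undefined term. This does not rescue it. The assistant's blind interview was over before there was an allocation to conceal. The researcher's blinding is described only in connection with random assignment, although the text does not say it ended there. Above all, blinding those who administer a questionnaire does not blind the person answering it.

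Several narrower points stand:
- That clients and caregivers knew their status is inferred from the design, though attending or waiting leaves no realistic alternative.
- Client self-rating is also an inference. Measures mentions observational measures without naming an instrument or observer, so the conclusion covers named measures only. Feasibility and the thematic analysis are outside it.
- The simulation rests on assumed inputs. Statistical Analysis does not say whether the Mann-Whitney test used change scores or post scores, and post scores give lower figures. At the smallest assumed bias the inflation is slight.
- Post-assessment is described only after group treatment, with no parallel waitlist assessment set out. The between-group argument therefore does not clearly extend to the Global Impression of Change, which asks about change following the group.
- Uncontrolled within-group changes have limits that blinding would not cure. Expectation is one explanation among others there.

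**Conclusion.** The concern holds. The documents claim a design property that the trial they describe lacks, and the gap affects all five named quantitative instruments. This follows from the text and does not depend on the simulation.

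The size of any bias cannot be derived from the documents. Under the stated assumptions, the between-group test on change scores would be significant with no true effect in about 6 to 15% of trials at 9 vs 9, about 6 to 14% at 12 vs 6, and about 5 to 11% at 7 vs 7. Without bias the exact test gives about 4%. At the top of the range that is 0.147/0.040, roughly 3.7 times the unbiased rate; on post scores alone it is 0.103/0.040, roughly 2.6 times. The label should be corrected because it changes how the effectiveness findings may be read.

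**What to change.** 1. In Present study, replace the double-blind label with *randomized, waitlist-controlled, open to clients and caregivers*.
2. State who was blinded, to what, and at what point. Include whether the post-assessment research assistants were blind to group.
3. In the analysis text and conclusions, say that differences on client- and caregiver-rated scales, within groups (Wilcoxon) and between groups (Mann-Whitney), cannot be separated from expectation.

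These are changes of wording, so they can be made although the study is written up as finished. No new data or analysis is needed, but the second item means checking the trial's records on the post-assessment staff. The downside is a more modest claim about effectiveness.

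### The plan does not say which groups, at which assessment, form the two sides of the between-group test; as described, the waitlist side would carry post-treatment scores

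*Combined protocol and SAP*

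**What the plan says.** Five statements bear on the comparison.

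- **Allocation (Procedure).** "Participants were initially allocated to either the treatment group or waitlist control group for one of the three sequential groups". The sentence names two conditions and three groups together.
- **Rounds of randomization (Procedure).** "Randomization occurred once a dozen participants were recruited and then again prior to the second group to accommodate rolling recruitment". Neither the allocation ratio nor the group sizes are given. On adherence: "All participants attended their assigned group except for one who requested an earlier group due to travel limitations"; there was also one replacement in the last group.
- **Baseline (Measures).** "The interview was completed prior to randomization to one of the three groups, and one month prior to group commencement".
- **Re-assessment (end of Measures).** "Following group treatment, interviews and post assessments were conducted by independent research assistants", with the window given as "within approximately four weeks of group completion". No assessment at the end of the waiting period is described.
- **Analysis (Statistical Analysis).** "group differences, within and between, were assessed using non-parametric analysis due to group composition i.e. Wilcoxon signed-rank and Man-Whitney U tests, respectively". Everyone who started the group is to be included. The section closes by saying that post-assessment data could not be obtained for one participant and one caregiver, so the sample size was 18.

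**The concern.** The opening section calls the study a randomized controlled trial and gives effectiveness as an aim beside feasibility. The between-group test is the only analysis that could use the randomization for that aim. A Mann-Whitney test needs two samples. Here there are three groups, each of which is eventually treated, and no rule turns them into a treated and an untreated sample.

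In a sequential waitlist design a later group is a control only while it is still waiting. What makes its score a control score is the time of measurement, not the label of the group. The plan gives the label but no measurement taken during the wait. If the post-assessments are analysed by allocated arm, treated people are compared with treated people. A null result would then say nothing about whether the program works, and a significant one could not be attributed to it.

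**Working it through.** **Inputs from the document.** 19 participants and 18 analysed; three sequential groups; two randomization rounds, the first at about 12 people; one described pre-assessment, before randomization; one described re-assessment, after group treatment; Mann-Whitney U between groups.

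**No design figure to reproduce.** The document gives no significance level, power, effect size, SD, allocation ratio, group sizes or sample-size calculation. Those used below are assumptions: two-sided exact test at 5%, normal scores with SD 1, effects of 0.8, 1.0 and 1.5 SD, and three groups of about 6.

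**Notation.** Let D be the treatment effect, the same in every group, with no effect before treatment and no time trend. Let n1, n2 and n3 be the sizes of groups 1, 2 and 3.

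**Step 1: every group scored after its own treatment (the schedule described).**
Treatment side = D and control side = D, so the contrast = D − D = 0 for any group sizes. Using change from baseline does not help, because each group's change also runs to its own post-treatment score. In simulation (20,000 runs, 6 v 12) the rejection rate was about 4% at all three effects (3.9%, 4.0%, 4.2%), which is just the false-positive rate of the exact test.

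**Step 2: part of the control side already treated.**
Suppose group 2 enters as control with post-treatment scores and group 3 enters untreated:

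contrast = D − D × n2/(n2 + n3) = D × n3/(n2 + n3)

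- Equal groups of 6: 6/12 = 0.50 D.
- Groups of 5 to 8 summing to 19, lowest: n2 = 8, n3 = 5 gives 5/13 = 0.38 D.
- Same range, highest: n2 = 5, n3 = 8 gives 8/13 = 0.62 D.

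The opposite error, counting a still-waiting group 2 as treated, gives D × n1/(n1 + n2), with the same range.

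**Step 3: who is a randomized control for group 1.**
About 12 people were in the first round, which leaves about 19 − 12 = 7 who came later. Because the second round was held to absorb rolling recruitment before the second group, those later recruits could not have been assigned to group 1. The randomized contrast for group 1 therefore rests on about 12 people, not 18.

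**Step 4: power by simulation.**

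| Comparison | 0.8 SD | 1.0 SD | 1.5 SD |
|---|---|---|---|
| 6 v 6, controls untreated | 21% | 30% | 59% |
| 6 v 12, all controls untreated | 28% | 41% | 74% |
| 6 v 12, half of controls already treated | 8% | 10% | 16% |

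Only the first row corresponds to people randomized together, and the 6 v 6 split is itself assumed. The 6 v 12 rows pool both rounds and only illustrate the loss from misclassification.

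**Step 5: can the baseline stand in as the control score?**
The one pre-group assessment described came before randomization. Comparing group 1's post-treatment scores with the waiters' baselines would mix the treatment effect with time and regression to the mean, which a waitlist is there to remove.

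**The case against.** The strongest reply is that the text is coherent. The allocation sentence reads naturally as a sequential waitlist design: people are first treated or waiting, and each attends one of three groups. The Measures sentence fixes when the interview took place and does not define an analysis factor. This stands. A reader might infer that the plan contradicts itself, making the middle group control in one section and treated in another. The document does not support that, because it gives the middle group no role anywhere. The fault is a missing definition, combined with an assessment schedule that supplies no untreated follow-up score.

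A reader might also infer that the plan halves the effect. Halving needs a treated group 2 pooled with an untreated group 3 of equal size, and the plan describes no such mix. The schedule it does describe gives zero. Nor does the plan propose pairwise tests among the three groups, so a multiplicity charge has no basis.

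Finally, waitlisted people may have been reassessed before their own group began without this being written down. That is possible: for someone randomized early to a later group, one interview may not have been both before randomization and one month before that group started. But only one pre-group assessment is described, and the plan would have to say that a second exists and that the test uses it.

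**Conclusion.** The concern holds as an undefined between-group contrast, and it should be corrected. Followed as written, the plan puts post-treatment scores on the waitlist side. The expected contrast is then zero if every group is scored after its own treatment. It is a diluted fraction of the effect if only some controls have been treated: about half for equal groups 2 and 3, and 0.38 to 0.62 for groups of 5 to 8. The zero rests on equal effects across groups and no time trend. The fractions rest on assumed group sizes, and the power figures also on an assumed effect, normal scores and a 5% level. That later recruits are not randomized controls for group 1 follows from the two rounds alone. The feasibility aim and the qualitative analysis are not affected.

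**What to change.** Use one definition in Procedure, Measures and Statistical Analysis:

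- The single between-arm Mann-Whitney comparison is group 1 against the people randomized with them in the first round to wait, by assigned group. The participant who moved to an earlier group is therefore counted as assigned.
- Control scores are those taken after randomization, before the control's own group starts, and close in time to group 1's post-assessment.
- No post-group score of a waitlisted participant enters the control sample, and the pre-randomization baseline is not used as the control outcome.
- If no post-randomization untreated score was collected, drop the between-arm effectiveness test, report the within-group pre-post results as uncontrolled, and state that no randomized contrast is available.

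The change itself is a rewording in three sections and, where suitable scores exist, a re-coding of the arm variable. The price is precision or scope. The comparison has about 12 people (for example 6 v 6, power about 30% at an assumed 1.0 SD effect), or the effectiveness conclusion becomes an uncontrolled one.

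### No repeat assessment over the wait is described; unless undescribed waiting scores exist, the planned tests give no controlled estimate for the effectiveness aim

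*Combined protocol and SAP*

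**What the plan says.** The Present study section describes a "pilot community-based, double blind, randomized controlled trial of an adapted DBT skills group" whose aim is to "empirically determine the feasibility and effectiveness of delivering an adapted DBT community-based skills group".

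On allocation, the Procedure section says: "Participants were initially allocated to either the treatment group or waitlist control group for one of the three sequential groups". There were two rounds: "Randomization occurred once a dozen participants were recruited and then again prior to the second group to accommodate rolling recruitment". Almost everyone was then treated: "All participants attended their assigned group except for one who requested an earlier group due to travel limitations and one replacement", the replacement being for the last group.

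On baseline, the Measures section says: "The interview was completed prior to randomization to one of the three groups, and one month prior to group commencement". The questionnaires follow that interview. On follow-up it says: "Following group treatment, interviews and post assessments were conducted by independent research assistants", within about four weeks of the group ending. People were asked what they had learned in the group and what had changed in their circumstances since attending, so this visit follows the person's own group.

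The Statistical Analysis section analyses everyone who started the group. It names a mixed ANOVA together with Wilcoxon signed-rank tests (within) and Mann-Whitney U tests (between). It does not say which groups, score or time point the between-group test uses, or whether the ANOVA was run as well as the rank tests or replaced by them.

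**The concern.** A waitlist controls for the passage of time only if waiting people are measured again while still untreated, over the same window as the treated people. The plan describes no such measurement. By the only described follow-up, the waitlist arm has had the group too.

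The effectiveness aim is at stake. A null difference between two treated arms would not show lack of benefit. A difference could reflect unequal time since baseline, or chance. A pre-post gain could reflect time, regression to the mean or concurrent care. The Participants section makes the last concrete: "All participants had regular therapy or treatment interventions with either assigned social workers" or other named professionals. Feasibility, client and caregiver experience, and the thematic analysis need no control score.

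**Working it through.** **1. The plan's own figure.** 19 enrolled (Participants) less 1 without a post-assessment (Statistical Analysis) = 18, which agrees with the stated N. The documents give no arm sizes, SDs, correlations, effect size or power.

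**2. What each test estimates.** Let δ be the treatment effect, and τ_A and τ_B the non-treatment change from baseline to post in the treatment-first and waitlist arms. If both arms have had the group by the post score and benefit equally:

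- Change in treatment-first arm = δ + τ_A
- Change in waitlist arm = δ + τ_B
- Wilcoxon, all 18: centred on δ plus the average τ. Benefit and drift cannot be separated.
- Mann-Whitney on change: (δ + τ_A) − (δ + τ_B) = τ_A − τ_B. The effect δ cancels. Post scores behave the same way if the arms have equal baseline means.
- Mixed ANOVA on the same two occasions: the time effect has the Wilcoxon problem and the group-by-time effect has the Mann-Whitney problem.

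This step needs no numbers.

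**3. Illustration under assumed drift.** Assumptions, none from the documents: normal scores, no treatment effect, pre-post correlation r of 0.6 or 0.7, and drift in baseline SDs. SD of change = √(2(1 − r)), which is 0.894 at r = 0.6 and 0.775 at r = 0.7. Share of simulated trials with two-sided p < 0.05:

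| Drift | Wilcoxon, n = 18 | ANOVA time effect (9 v 9 or 6 v 12) |
|---|---|---|
| 0.1 | 7-8% | 7-8% |
| 0.2 | 14-17% | 13-18% |
| 0.3 | 26-33% | 24-34% |
| 0.5 | 59-71% | 56-73% |

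With equal benefit and equal drift in the two arms, Mann-Whitney on change rejects in about 4% of trials and group-by-time in 5%, whatever the benefit. That restates step 2.

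**4. What a controlled contrast could deliver.** Suppose repeat waiting scores exist. For treated change v still-waiting change, the 95% CI half-width is t × √(2(1 − r)) / √(Σ n₁n₂/(n₁ + n₂)), summed over rounds.

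*First dozen only* (Procedure; the splits 6 v 6 and 4 v 8 are assumed), t on 10 df = 2.228:

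- 6 v 6, r = 0.7: 2.228 × 0.775 / √3.000 = 1.00
- 4 v 8, r = 0.6: 2.228 × 0.894 / √2.667 = 1.22
- Exact rank-test power at an effect of 1.0 baseline SD: 36% and 46% (6 v 6) and 35% and 44% (4 v 8), at r = 0.6 and 0.7

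*Adding a second round with its own waiting comparison.* The documents do not state that it had one. Its size of 7 is 19 − 12, or fewer to allow for the replacement and the missing post-assessment.

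- 6 v 6 + 3 v 4, r = 0.7: 2.120 × 0.775 / √4.714 = 0.76
- 4 v 8 + 2 v 3, r = 0.6: 2.145 × 0.894 / √3.867 = 0.98
- Stratified rank-test (van Elteren) power at 1.0 SD: about 47-70%

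**The case against.** The best counter-argument lies in the baseline timing. The interview is placed both before randomization and one month before group commencement. If the second phrase means the person's own group, a later-group baseline is an untreated score taken late in the wait, and treated post scores could be set against it. A reader might therefore infer too much from the claim that the waitlist was never measured while untreated; the documents do not support that. What is missing is a described *repeat* score over the wait. The own-group reading also fits poorly with a single pre-randomization interview for first-round people sent to later groups. Even if it is right, it gives no waiting change, and the plan does not say the score is used as a control.

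A second objection is that treated v treated is inferred. The between-group contrast is undefined, and naming a waitlist and a between-group test suggests that some controlled comparison was intended. This stands as a reason for conditional wording. It does not supply a contrast.

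A reader might also infer that the sponsor will present uncontrolled results as randomized evidence. The documents contain no such report; the randomized-controlled and effectiveness labels make misreading a risk only.

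Finally, the drift figures follow from the drift chosen. They do not measure bias in this trial.

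**Conclusion.** The point holds in conditional form. One baseline with ambiguous timing and one re-assessment after the person's own group are described, with no repeat score over the wait. Unless undescribed end-of-wait scores exist, none of the named analyses gives a controlled estimate of effectiveness. That rests on the described schedule, on nearly everyone having attended their group, and on the analysis set being those who started it; no assumed number is needed.

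It must be resolved before any effectiveness claim, because the answer decides what can be concluded. Confidence is medium, since a short methods text may omit assessments that took place. If repeat scores do exist, the first dozen alone would give a half-width of about 1.0-1.2 baseline SD. About 0.8-1.0 SD is reachable only if the second round had its own treated v waiting comparison. Both ranges depend on the assumed r and splits.

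**What to change.** State when each baseline was taken relative to randomization and to the person's own group start, and whether any untreated waiting scores exist. Define the between-group contrast (groups, score, time point) and say whether the mixed ANOVA was run or replaced by the rank tests. Then:

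- **No untreated waiting scores.** Drop the between-group test as evidence of effectiveness. Report uncontrolled pre-post change that may reflect time, regression to the mean or concurrent care.
- **Repeat waiting scores exist.** Make the main contrast treated change v still-waiting change over the same window, by randomized allocation within randomization round (for example an exact van Elteren test). Analyse the switcher as assigned. Leave the replacement out of this contrast unless randomized, and state that this departs from the analysis set of everyone who started the group. Report an estimate with a confidence interval.
- **Only a late-wait baseline exists.** Only a raw-score comparison is possible: treated post score v waiting baseline.

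The cost is a table of assessment dates by round and group, revised wording and, where scores allow, a re-analysis. No new data are needed. The downside is a weaker effectiveness claim, or a controlled but imprecise one.
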